4.1 Screening period

It is recommended the screening assessments be performed in a stepwise process beginning with the confirmation of T790M mutation status as determined by the designated central laboratory. However, screening assessments may be done in parallel to the T790M mutation assessment, as appropriate. Procedures will be performed according to the Study Plan (See [Table 1](#)). Tumour assessments and other clinical data obtained as standard of care prior to consent may be used for the study provided the assessments fall within the protocol specified period prior to the first dose of the study treatment.

At screening, consenting subjects are assessed to ensure that they meet eligibility criteria. Subjects who do not meet these criteria must not be enrolled in the study. Demographic data and other characteristics will be recorded and will include date of birth or age, gender, smoking history, race and/or ethnicity according to local regulations.

Patients will be considered in screening period until all Visit 1 assessments are completed and eligibility is confirmed. Patients will be considered enrolled and in the treatment period once AZD9291 therapy has been initiated.

Mandatory screening tumour biopsy sample for mutation analysis:

Tumour sample must be formalin fixed and paraffin embedded (FFPE) and must be biopsied following progression on the latest line of therapy. Samples may be collected from primary or metastatic tumour deposits. Bone samples (including soft tissue tumoural masses emerging from the bone) cannot be accepted for testing. Sites should ship the FFPE tumour sample to the testing laboratory as soon as it is available. Tissue should be less than 60 days old from date of sectioning to date of testing. Blocks must be provided wherever possible. If this is not possible, 12-20 slides of freshly prepared unstained 5-micron sections from this screening tumour block may be provided. See [Section 5.6](#).

The mandatory screening tumour biopsy must not be taken from a previously irradiated lesion (Please refer to Inclusion criterion number 9 for details). This biopsy sample is not subject to the 28-day screening window; if tissue is already available from a biopsy taken since confirmation of disease progression on the most recent treatment regimen then there is no need for a further biopsy as this sample can be submitted for T790M mutation status. If the first biopsy is not confirmed as T790M mutation positive due to test failure (i.e. an invalid result or invalid run occurred), testing will be repeated and an additional biopsy sample may be requested. If the T790M mutation is not detected in the first biopsy (and the cobas® EGFR Mutation Test indicates a valid result), no additional testing for the subject will be performed for this study and an additional biopsy sample WILL NOT be accepted.

Optional second tissue sample for diagnostic development:

The optional second tissue sample (FFPE) may be provided to facilitate diagnostic development and pre-market approval of the diagnostic test. This should be obtained at the same time and as part of the same procedure as the mandatory screening biopsy.

Written informed consent/Assignment of subject enrolment number:

Each potential subject will provide informed consent prior to starting any study specific procedures (see Section 10 of this Clinical Study Protocol for Ethics and Regulatory Requirements). All subjects will be required to provide consent to supply a new tumour biopsy sample entry into this study. This consent is included in the main subject informed consent form. However, please note that patients are asked to provide separate consent for provision of optional tumour biopsy samples, if willing (see Section 5.6).

Once consent has been signed, the PI or delegate, will contact IVRS/IWRS to have the subject assigned a unique enrolment number.

WHO Performance Status:

Performance status will be assessed at the visits indicated in the Study Plan (see Table 1 and Table 2) according to WHO criteria as follows:

- 0 = Fully active, able to carry out all pre-disease activities without restrictions
- 1 = Restricted in physically strenuous activity but ambulatory and able to carry out work of a light or sedentary nature eg, light housework, office work
- 2 = Ambulatory and capable of self-care, but unable to carry out any work activities. Up and about more than 50% of waking hours
- 3 = Capable of only limited self-care, confined to bed or chair more than 50% of waking hours
- 4 = Completely disabled, cannot carry on self-care, totally confined to bed or chair

4.2 Treatment period

A cycle of treatment is defined as 21 days of once daily AZD9291 treatment. After Cycle 7 Day 1, the duration between study visits will change from every 21 days (3 weeks) to every 42 days (6 weeks).

If a patient continues to receive treatment with AZD9291 beyond RECIST 1.1 defined progression they must continue to follow the Treatment visit schedule and assessments excluding study specific RECIST 1.1 assessments.

Descriptions of the procedures for this period are included in the Study Plan (see Table 1 and Table 2).

After final DCO (i.e. after final data cut-off date), patients may continue to receive AZD9291, if in the opinion of their treating physician they are continuing to derive clinical benefit from continued treatment, the period is defined as continued access. (see Section 4.4 and Section 7.8)

4.3 Follow-up period

4.3.1 Discontinuation visit

A Discontinuation Visit will be performed at the time AZD9291 is permanently stopped. Refer to [Table 1](#) and [Table 2](#) for full details.

4.3.2 28 Day follow-up

As a minimum, telephone contact should be made with the patient 28 days (+/-7 days) following the discontinuation of AZD9291 to collect new AEs and follow up on any ongoing AEs and concomitant medications (including any subsequent cancer therapy). Refer to [Section 6.3](#) for full details on AE recordings during follow-up.

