6.3 Recording of adverse events

6.3.1 Time period for collection of adverse events

Adverse Events will be collected from time of signature of informed consent throughout the treatment period and including the safety follow-up period. The follow-up period is defined as 28 days after study treatment is discontinued. SAEs occurring in the follow-up period should be reported to AstraZeneca in the usual manner (see Section 6.4).

Following discontinuation of AZD9291, SAEs considered related to study procedures should continue to be collected as outlined in [Table 6](#)

After the final DCO, there may be some patients remaining on study treatment. For these patients who are continuing to receive AZD9291 AstraZeneca will collect information (during the treatment period and for 30 days safety follow up after last dose) on SAEs, deaths (including those due to disease progression), pregnancy, overdose, discontinuation due to AEs/SAEs and drug accountability only.

Table 6 Summary of recording and follow-up of adverse events and deaths

	Consent to Treatment Period	Until 28-day Follow-up Visit (safety follow-up period)	Post 28-day Follow-up visit but prior to progression (if applicable)	Post 28-day Follow-up visit and post progression (survival follow-up period)
Collect all new AEs in CRF	Yes	Yes	No	No
Collect all ongoing AEs in CRF	Yes	Yes	Yes	Yes
Collect all study procedure-related SAEs in CRF	Yes	Yes	Yes	Yes
Death due to AE, or unknown cause ^a	Yes	Yes	No	No

^a For example, death not due to disease progression, refer to Section 6.3.10

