6.3.2 Follow-up of unresolved adverse events

Any AEs that are unresolved are followed up by the investigator for as long as medically indicated. AstraZeneca retains the right to request additional information for any patient with ongoing AE(s) /SAE(s) at the end of the study, if judged necessary.

If an investigator learns of any SAEs, including death, at any time and he/she considers there is a reasonable possibility that the event is related to AZD9291, the investigator should notify AstraZeneca.

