8.5 Calculation or derivation of safety variable(s)

Adverse events

Adverse Events (both in terms of MedDRA preferred terms and CTCAE grade) will be listed individually by patient.

Any AE occurring before treatment with AZD9291 will be included in the data listings but will not be included in the summary tables of AEs.

Any AE occurring within 28 days of discontinuation of investigational product (ie, the last dose of AZD9291) will be included in the AE summaries. Any events in this period that occur after a patient has received further therapy for cancer (following discontinuation of AZD9291) will be flagged in the data listings.

A separate data listing of AEs occurring more than 28 days after discontinuation of AZD9291 will be produced. These events will not be included in AE summaries

Other significant adverse events (OAEs)

During the evaluation of the AE data, an AstraZeneca medically qualified expert will review the list of AEs that were not reported as SAEs and AEs leading to discontinuation. Based on the expert's judgement, significant AEs of particular clinical importance may, after consultation with the Global Patient Safety Physician, be considered OAEs and reported as such in the CSR. A similar review of laboratory/vital signs/ECG data will be performed for identification of OAEs.

Examples of these could be marked haematological and other laboratory abnormalities, and certain events that lead to intervention (other than those already classified as serious), dose reduction or significant additional treatment.

Safety Assessments

For change from baseline summaries for vital signs, laboratory data, LVEF, ECGs and physical examination, the baseline value will be the latest result obtained prior to the start of investigational product.

The denominator used in laboratory summaries will only include evaluable patients, in other words those who had sufficient data to have the possibility of an abnormality.

For example:

- If a CTCAE criterion involves a change from baseline, evaluable patients would have both a pre-dose and at least 1 post-dose value recorded
- If a CTCAE criterion does not consider changes from baseline, to be evaluable the patient need only have 1 post dose-value recorded

The denominator in vital signs data should include only those patients with recorded data.

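### The safety follow-up call may fall on days 21-27 and Table 6 ends new-AE collection there, but the follow-up period and the AE summaries run to day 28

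*Protocol*

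**What the plan says.** Four places in the protocol govern AEs after treatment stops.

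- **Section 4.3.2 (28 Day follow-up)** sets the minimum contact: "telephone contact should be made with the patient 28 days (+/-7 days) following the discontinuation of AZD9291 to collect new AEs". It refers to Section 6.3 for the details of AE recording. The 28-day follow-up column of Tables 1 and 2 carries the same window of 7 days either side.
- **Section 6.3.1 (text)** has AEs collected from consent "throughout the treatment period and including the safety follow-up period", and states: "The follow-up period is defined as 28 days after study treatment is discontinued".
- **Section 6.3.1 (Table 6)** heads the corresponding column "Until 28-day Follow-up Visit (safety follow-up period"). The row "Collect all new AEs in CRF" is answered Yes up to that visit and No in both later columns, before and after progression. The row for deaths due to an AE or of unknown cause has the same pattern.
- **Section 8.5** sets the analysis window: "Any AE occurring within 28 days of discontinuation of investigational product (ie, the last dose of AZD9291) will be included in the AE summaries". Later events are kept apart: "A separate data listing of AEs occurring more than 28 days after discontinuation of AZD9291 will be produced".

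**The concern.** One period has two end points. In the definition and in the analysis it ends on a calendar day, day 28. In the data-collection table it ends at a contact that may come a week earlier. After an early call, an AE that starts before day 28 belongs in the summaries, yet Table 6 tells the site not to collect it as new and no scheduled contact asks about it.

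Safety and tolerability are a secondary objective, reported with the objective response rate at the primary analysis and updated later. If the last days of the window are observed for some patients and not for others, the AE counts depend in part on when sites happened to call. Any resulting error is an under-count.

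**Working it through.** The protocol states no figure for this point, so there is none to reproduce. The check is day arithmetic and a comparison of the passages.

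**Inputs**
- Nominal contact: day 28 after discontinuation, 7 days either side (Section 4.3.2; Tables 1 and 2).
- End of new-AE collection: the contact itself, on day *d* (Table 6).
- End of the defined follow-up period and of the summary window: day 28 (Sections 6.3.1 and 8.5).

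**Permitted contact days**
- Earliest: 28 − 7 = day 21.
- Latest: 28 + 7 = day 35.

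**Days of the summarised window with no scheduled new-AE contact:** max(0, 28 − *d*)

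| Contact day *d* | Days uncovered | Share of 28 days |
|---|---|---|
| 21 | 7 | 7/28 = 25% |
| 22 | 6 | 6/28 = 21% |
| 24 | 4 | 4/28 = 14% |
| 27 | 1 | 1/28 = 4% |
| 28 to 35 | 0 | 0% |

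**Do late calls offset early ones?** No. Events that start after day 28 go to the separate listing in Section 8.5 and stay out of the summaries. The symmetric window therefore has a one-sided effect.

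**Average loss.** This needs the distribution of call days, which the protocol does not give. If all calls fall on or after day 28, the loss is 0%. If all fall on day 21, it is 25%. As an illustration only, an even spread over days 21-35 puts half the calls before day 28 with a mean shortfall of 3.5 days: 0.5 × 3.5 = 1.75 days, and 1.75/28 is about 6%. Nothing in the protocol supports that spread over any other.

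**Does a later contact close the gap?** Progression follow-up (Section 4.3.3) refers back to Table 6. Survival follow-up (Section 4.3.4) lists no new-AE collection. Table 1's footnote on the period after discontinuation covers only serious events related to study procedures. The text of Table 2 available for this review breaks off before any AE row, so that table could not be checked beyond its window row.

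**What is still captured after an early call?**
- Serious AEs within the 28 days: reportable under the text of Section 6.3.1. Section 6.4 requires all serious AEs to be reported whatever their causality.
- Deaths within the follow-up period: Section 6.3.10 requires them to be reported. Table 6 conflicts with this, because it answers No for AE deaths after the visit. After a day-21 call, an AE death on day 25 is No in Table 6 and reportable under Section 6.3.10.
- Ongoing AEs and procedure-related serious AEs: Table 6 continues both.
- Serious AEs at any later time: Section 6.3.2 asks for notification when the investigator learns of one "at any time and he/she considers there is a reasonable possibility that the event is related to AZD9291".

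What remains is new non-serious AEs with onset on days 22-28, and serious events in those days that the site would learn of only if a contact prompted it.

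**The case against.** The strongest reply is that the collection rule is already 28 days. The text of Section 6.3.1 says so, Table 6 labels its column as the safety follow-up period, and Section 4.3.2 sets the call only as a minimum and defers to Section 6.3. On that reading the 7 days are a scheduling tolerance, and a site that closes collection on day 21 departs from Section 6.3.1. Part of this stands: the text does require 28 days. But Section 4.3.2 allows further contact without requiring it, and Table 6 answers No after the visit. The instructions contradict each other, and the text alone does not cure that.

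The case against larger claims is sound. Four stronger readings are tempting and are not supported:

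- *Serious AEs judged unrelated to the drug go unreported.* Sections 6.3.1 and 6.4 require them regardless of causality. Only discovery is at risk.
- *AE rates use a denominator that wrongly assumes 28 days of observation.* Section 8.7.2 plans the number of patients with each AE by grade. The protocol states no person-time rate.
- *Patients who stop because of progression are especially exposed.* Table 6 answers No both before and after progression.
- *A typical loss of about 6%, or one near 25%, is to be expected.* Each depends on an assumed pattern of calls.

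It is also fair that a lost day is not a lost event. A summary count changes only if the missed AE would have been the patient's first of its kind or the highest grade, and treatment before it has no fixed maximum duration. The trial has a single arm, so no between-arm safety comparison can be distorted.

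**Conclusion.** The contradiction is real and modest in reach. Section 4.3.2 with Table 6 lets new-AE collection end 1 to 7 days before the window that Section 6.3.1 defines and Section 8.5 summarises. Per patient, 0 to 7 of 28 days (0-25%) lack a scheduled contact to collect new AEs. The figure depends wholly on call timing, and the number of events missed cannot be estimated from the protocol. Table 6 also needs reconciling with Section 6.3.10 on AE deaths after the visit.

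The conclusion assumes that some sites call before day 28 and follow Table 6 as printed. If every call falls on or after day 28, nothing is lost. The primary endpoint is unaffected. The point merits action because the correction is cheap and makes collection cover the period that is summarised.

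**What to change.** - In Section 4.3.2, and in the 28-day follow-up column of Tables 1 and 2, make the window one-sided: 28 days (+7 days).
- In Table 6, end new-AE collection, and the row for deaths due to an AE or of unknown cause, at 28 days after the last dose, as ascertained at the follow-up contact. This agrees with Sections 6.3.1, 6.3.10 and 8.5.

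The change is wording in one section and three tables, with no extra visit or contact. The cost is scheduling: permitted call days fall from 15 (days 21-35) to 8 (days 28-35). Onsets on days 29-35 mentioned at a later call would no longer be collected as new AEs. They never enter the summaries. If the sponsor wants them for the separate listing, Table 6 should say so.

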4.3.3 Progression follow-up

Patients who discontinue AZD9291 for reasons other than progression will continue RECIST 1.1 assessments every 6 weeks (relative to first dose of AZD9291) for objective progression prior to RECIST modules freeze time (24 months post LSFD). The last tumour assessment data at 24 months post LSFD should be entered into RAVE per eCRF entering guidance. In addition to RECIST 1.1 assessments, the following assessments are also required during this follow-up period as detailed in the Study Plan (see [Table 1](#)):

Prior to RECIST modules freeze time:

- EORTC QLQ-C30 and EQ-5D-5L every 6 weeks and at the time of progression.
- EORTC QLQ LC13 and PRO-CTCAE every 3 weeks and at the time of progression.
- Plasma for ctDNA collected every 6 weeks up to and including progression (corresponding with the RECIST 1.1 assessments – and continuing after treatment discontinuation if this is in absence of progression)
- Adverse event collection detailed in [Table 6](#)
- Anti-cancer therapy collected every 6 weeks.

Change after RECIST modules freeze time:

- After RECIST modules freeze time, the sites will continue to perform tumour investigator's assessments every 12 weeks according to their local practice, both central imaging scans and investigator assessment data will not be collected into eCRF. Please refer to [Table 2](#).
- Plasma for ctDNA collected every 12 weeks up to and including progression (corresponding with the RECIST 1.1 assessments – and continuing after treatment discontinuation if this is in absence of progression). Please refer to [Table 2](#).

4.3.4 Survival follow-up

- Assessments for survival should be made every 6 weeks (relative to first dose) following objective disease progression or withdrawal from treatment. Survival information may be obtained via telephone contact with the patient, patient's family or by contact with the patient's current physician. In addition to the survival status, the following assessments are also required post progression as detailed in the study plan (see [Table 1](#) and [Table 2](#)):
- EORTC QLQ-C30 and EQ-5D-5L every 6 weeks.
- EORTC QLQ LC13 and PRO-CTCAE every 3 weeks.
- Anti-cancer therapy collected every 6 weeks.
- Subsequent response/progression data every 6 weeks until the first confirmed disease progression on a subsequent treatment.

Survival data will be collected up to the time of the final OS analysis. Patients should be contacted in the 2 weeks following the data cut-off for the final survival analyses to provide complete survival data.

The status of ongoing, withdrawn (from the study) and "lost to follow-up" patients at the time of an overall survival analysis should be obtained by the site personnel by checking the patients notes, hospital records, contacting the patients general practitioner and checking publicly available death registries. In the event that the patient has actively withdrawn consent to the processing of their personal data, the vital status of the patient can be obtained by site personnel from publicly available resources where it is possible to do so under applicable local laws.

4.4 Patient management in the continued access period (post final DCO)

The final analysis of the study will be performed based upon a DCO when approximately 95 death events (55% maturity) for the overall survival is reached.

At this time point, the clinical study database will close to new data. Patients are, however, permitted to continue to receive study treatment beyond the closure of the database if in the opinion of the investigator they are continuing to receive benefit from treatment. Dispensing of study treatment post final OS analysis DCO will be recorded outside of IWRS/IVRS. Patients who remain on study treatment after this time point will be monitored according to routine clinical practice as defined by the investigator. At routine clinic visits, patients will return the unused medication, and a thorough drug accountability assessment will be performed at the site.

For patients who do continue to receive treatment beyond the time of this data cut off, investigators will continue to report all SAEs, overdose and pregnancies to AstraZeneca via paper and emailed (preferably) or faxed directly to TCS in accordance with section [6.4](#), [6.5](#)

and 6.6. All SAEs, overdoses and pregnancies would be reported until 30 days after last dose. If an investigator learns of any SAEs, including death, at any time after a patient has completed the study, and he/she considers there is a reasonable possibility that the event is casually related to the IP, the investigator should notify AstraZeneca (see Section 6.4). Additionally, as stated in section 6.3, any SAE or non-serious AE that is ongoing at the time of this DCO, must be followed up to resolution unless the event is considered by the investigator to be unlikely to resolve, or the patient is lost to follow up.

Study would be open until last patient treated. Final Last Subject Last visit will be defined as the last visit after last patient's treatment discontinuation.

If study drug would be approved on market for use in disease under study indication, patients may be discontinued and switched to market product. Drug supply options can be available depending on the country and would be proposed to patient when found as best way to continue treatment by both AZ and investigator.

